14.1. Interim Analysis	
15. References	

Table of Contents		
Table		Page
Table JZGB.7.1.	Schedule of Analyses	16
Table JZGB.10.1.	Patient Exposure Prior to Maintenance Period	21

Table of Contents			
Figure		Page	
Figure JZGB.6.1.	ARM 1: pegilodecakin +FOLFOX.	12	
Figure JZGB.6.2.	ARM 2: FOLFOX alone.	13	

3. Revision History

Statistical analysis plan (SAP) Version 1 was approved prior to Lilly study team unblinded to study results.

4. Introduction

This is a randomized, open-label, global Phase 3 study. This document describes the planned statistical analyses for protocol J1L-AM-JZGB (JZGB), A Randomized Phase 3 Study of AM0010 in Combination with FOLFOX Compared with FOLFOX Alone as Second-line Therapy in Patients with Metastatic Pancreatic Cancer that has Progressed During or Following a First-Line Gemcitabine Containing Regimen. Any deviations from the analysis plan will be described in the clinical study report. Study JZGB is also known as "SEQUIOIA" and "AM0010-301." AM0010 is also known as pegilodecakin or LY3500518.

5. Study Objectives

5.1. Primary Objective

To compare the efficacy of pegilodecakin in combination with FOLFOX versus FOLFOX alone in patients with metastatic pancreatic cancer as measured by overall survival (OS)

5.2. Secondary Objectives

- To compare the efficacy of pegilodecakin in combination with FOLFOX versus FOLFOX alone in patients with metastatic pancreatic cancer as measured by:
 - progression-free survival (PFS)
 - Objective response rate (ORR), disease control rate (DCR), Duration of Response (DoR) by RECIST v1.1
 - One-year overall survival rate.
- To compare the safety and tolerability of Pegilodecakin in combination with FOLFOX versus FOLFOX alone.

5.3. Exploratory Objectives

- To explore biomarkers that may correlate with tumor response, immune activation, and relationships to clinical efficacy outcomes.
- Study the immunogenicity of anti-drug antibody of pegilodecakin.
- To explore associations between patient-reported symptoms, functioning, and global health status/Quality of Life (QoL) using the European Organisation for Research and Treatment (EORTC) Quality of Life of cancer Patients (QLQ-C30) questionnaire as well as current health status and the EuroQol-5D (EQ-5D) Index used in the economic evaluation of health care using the 5-level EQ-5D (EQ-5D-5L) questionnaire.

6. Investigational Plan

6.1. Overall Study Design and Plan

This is a randomized, open label, global Phase 3 study of AM0010(pegilodecakin) in combination with FOLFOX compared with FOLFOX alone as second-line therapy in patients with advanced metastatic pancreatic cancer that has progressed during or following a first-line genetiabine containing regimen.

Approximately 566 patients will be randomized. Two interim analyses are planned. The first interim analysis will be performed when at least 60 randomized patients have had the opportunity to receive 4-months of therapy from the date of randomization. Based on the first interim analysis, the Data Monitoring Committee (DMC) will review the pharmacokinetic (PK) exposure-safety and PK exposure-efficacy on the composite aggregate data for a Go/No Go decision to enroll the entire Phase 3 study.

The second interim analysis will occur when approximately 276 deaths (70% of total 393 deaths needed for final analysis) have occurred. Based on the second interim analysis, the DMC will inform the study team whether the interim boundary are met and recommend modifying, completing, or discontinuing the trial.

Patients will be randomized in a 1:1 ratio to pegilodecakin combined with FOLFOX or FOLFOX alone.

The randomization will be stratified by 2 stratification factors:

- prior single agent gemcitabine therapy versus gemcitabine/nab-paclitaxel therapy
- North America versus Europe versus Asia-Pacific(APAC)

6.2. Study Endpoints

6.2.1. Primary Endpoint

The primary endpoint of this study is OS as defined as the time from date of randomization to death due to any cause.

6.2.2. Secondary Endpoints

The secondary endpoints of the study include:

- Progression-free survival is defined as the time from date of randomization to the earlier of first documentation of definitive disease progression (if the initial progressive disease [PD] is pseudopregression, it need to be confirmed by the consecutive scan) or death due to any cause.
- Objective response rate is defined as the proportion of patients who achieve a confirmed complete response (CR) or partial response (PR) as assessed by Response Evaluation Criteria in Solid Tumors (RECIST) v1.1.

- Duration of Response is defined as the time from the date of the first documentation of objective tumor response (CR or PR) to the date of the first documentation of objective tumor progression or death due to any cause, whichever occurs first.
- One-year OS rate is defined as the survival rate as estimated using the Kaplan-Meier method at the end of the first year.
- Compare the safety and tolerability of pegilodecakin in combination with FOLFOX versus FOLFOX alone.

6.2.3. Exploratory Endpoints

The exploratory endpoints of the study include:

[figure not shown]
- Change from baseline for serum CA19-9.
- In addition to baseline and change from baseline in the EORTC core questionnaire, the (QLQ-C30), (EORTC QLQ-C30) and EuroQol Group 5-dimension 5-level measure of health-related quality of life (EQ-5D-5L Index score and Visual Analog Score [VAS] score). Time to deterioration in EORTC QLQ-C30 patient-reported symptoms and functioning will be explored using symptom items that correspond with the treatment-emergent adverse event (TEAE) profile (eg, fatigue, anorexia, and nausea/vomiting) as well as the subscales for functioning and Health-Related Quality of Life (HRQoL).
- Pegilodecakin PK (sparse sampling) in pancreatic cancer patients and immunogenicity .

6.3. Treatments

ARM 1: AM0010(pegilodecakin) (5 μ g/kg) SQ dosed on Days 1–5 (with rest on Days 6 and 7) and Days 8-12 SQ (with rest on Days 13 and 14) plus FOLFOX (dl-LV 400 mg/m² and oxaliplatin 85 mg/m² followed by bolus 5-FU 400 mg/m² and a 46- to 48-hour infusion of 5-FU 2400 mg/m²) initiated on Day 1 of a 14-day cycle, for up to 12 cycles or until disease progression by RECIST v.1.1.

While receiving FOLFOX during Cycles 1–12, pegilodecakin at 5 μ g/kg will be administered as 1 of 2 fixed doses, either 0.4 mg for patients weighing ≤ 80 kg or 0.8 mg for patients weighing ≥ 80 kg.

Patients in ARM 1 may continue on maintenance cycles with pegilodecakin (see Figure JZGB.6.1). After discontinuation of FOLFOX in the absence of tumor progression (ie, completion of the planned 12 cycles or unacceptable FOLFOX related toxicity), pegilodecakin at 10 μ g/kg will be administered as 1 of 2 fixed doses, either 0.8 mg for patients weighing \leq 80 kg or 1.6 mg for patients weighing \geq 80 kg.

[figure not shown]

ARM 1: AM0010 + FOLFOX

Figure JZGB.6.1. ARM 1: pegilodecakin +FOLFOX.

ARM 2: Patients receive only FOLFOX which is initiated on Day 1 of a 14-day cycle, for up to 12 cycles or until disease progression by RECIST v.1.1 (see Figure JZGB.6.2).

Abbreviations: F-FU = 5-fluorouracil; IV = intravenous.

Figure JZGB.6.2. ARM 2: FOLFOX alone.

Crossover of patients from the FOLFOX treatment arm into the FOLFOX plus pegilodecakin treatment arm is not permitted. Supportive care per the institution's normal standard of care, including concomitant medications, can be provided at the Investigator's discretion.

6.4. Treatment Duration

Each cycle is 14 days, with Days 6, 7, 13, and 14 being rest days for pegilodecakin. FOLFOX will be administered on Day 1 of each cycle. Patients randomized to the investigational combination treatment (pegilodecakin plus FOLFOX) ARM 1, after completion of up to 12 cycles of combination chemotherapy or if experiencing chemotherapy intolerance (as defined as Grade 3 or 4 non-hematologic toxicity that has not resolved to baseline in 28 days or Grade 4 hematologic toxicity that has not resolved to baseline in 28 days) may continue to receive maintenance pegilodecakin if the patient continues to receive clinical benefit (CR, PR, or stable disease [SD]). Patients will be treated until tumor progression by RECIST v.1.1. For ARM 2 (FOLFOX only) patients may receive FOLFOX for up to 12 cycles or 24 weeks or until tumor progression by RECISIT v.1.1 or until patients experience unacceptable toxicity, require palliative radiotherapy, withdraw consent, or their physician feels it is no longer in their best interest to continue on study treatments whichever occurs earlier.

To mitigate the chance of detecting false-progression (ie, pseudoprogression) early in the course of treatment on ARM 1 with pegilodecakin in combination with FOLFOX, patients whose scans show radiographic progression in the absence of clinical deterioration including worsening Eastern Cooperative Oncology Group (ECOG) Performance Status (PS) as assessed by the Investigator may remain on study treatments and should have an additional scan 4 weeks (±3 days) later as outlined in protocol Section 8.1.1. If this subsequent scan shows disease progression, the patient will be discontinued from study treatments.

7. General Statistical Considerations

7.1. Population:

The enrolled population includes all patients who sign the informed consent document.

The intent-to-treat (ITT) population includes all randomized patients per interactive voice response system (IVRS).

The safety population includes all randomized patients who received any amount of pegilodecakin or FOLFOX.

Per-Protocol Population: All patients who are in the safety population and have no major protocol deviations.

The major protocol deviations which will result in exclusion from the Per-Protocol population are listed below. This is not an exhausted list and may be amended over the course of the trial.

- patients with disease other than metastatic pancreatic adenocarcinoma
- patients with ECOG >1 at baseline
- patients who received more than 1 prior regimen in metastatic setting
- patients who do not have measurable disease at baseline
- patients who received the incorrect randomized treatment assignment (for any duration)

Anti-drug antibody (ADA) evaluable population includes all patients with at least 1 baseline and postbaseline ADA assessment.

Response evaluable population includes patients who have at least 1 baseline tumor scan and 1 adequate postbaseline tumor scan.

Unless otherwise noted, all disposition analyses will be performed on the enrolled population, all patient characteristic and efficacy analyses will be performed on the ITT population, and all safety and exposure analyses will be performed on the safety population.

All analyses will be performed by treatment arm. Unless otherwise noted, all analyses on the ITT population will be performed by assigned treatment arm and all analyses on the safety population will be performed by actual treatment received.

7.2. Definitions and Conventions

The **date of randomization** is the date the patient was randomly assigned to pegilodecakin + FOLFOX arm or FOLFOX arm using the IVRS.

The **date of first dose** is the date of the first dose of pegilodecakin or any component of FOLFOX whichever is earliest.

The **baseline value assessment** for safety **in general** is the last value observed on or prior to the first dose of pegilodecakin or FOLFOX. For efficacy, the baseline value assessment is the last

value on or prior to the randomization date or the first value on or prior to the first dose of pegilodecakin or FOLFOX whichever occurs earlier.

The change from baseline will be calculated by subtracting the baseline values from the individual post-treatment values. If either the baseline or post-treatment value is missing, the change from baseline is set to missing.

The study day of a safety event or assessment will be calculated as:

- The difference between the date of the event or assessment and the date of first dose plus 1 for all events or assessments occurring on or after the day of first dose. For example, if an event occurs on 08 June 2014 and the date of first dose was 06 June 2014, the study day of the event is 3.
- The difference between the date of the event or assessment and the date of first dose for all events or assessments occurring before the day of first dose. For example, if an event occurs on 05 June 2014 and the date of first dose was 06 June 2014, the study day of the event is -1.

The study day of an efficacy event or assessment will be calculated as:

- the difference between the date of the event or assessment and the date of randomization plus 1 for all events or assessments occurring on or after the date of randomization
- the difference between the date of the event or assessment and the date of randomization for all events or assessments occurring before the date of randomization.

One month = 30.4375 days

One year = 365.25 days

Unless otherwise noted, summaries of continuous variables will include a mean, median, standard deviation, minimum, and maximum.

Unless otherwise noted, summaries of categorical variables will include the frequency and percentage (relative to the population being analyzed) of each category.

Visit window approaches will not be used for this study. Visit based summaries will include scheduled assessments only. All scheduled and unscheduled post-baseline assessments will be used for derivation of minimum, maximum, and worst-case post-baseline values. All available data will be listed.

P-values will be rounded to 4 decimal places. P-values that round to 0.0000 will be presented as '<0.0001' and p-values that round to 1.000 will be presented as '>0.9999.' Confidence intervals (CIs) will be presented as 2-sided 95% CIs unless specified differently in specific analysis.

All data listings will present subjects in the ITT population, unless otherwise noted. For data listings, imputed dates will not be included and only the actual reported values will be displayed. As applicable, durations will be calculated and presented using imputed dates. When this occurs, a footnote will be added to the data listing indicating this.

7.3. Sample Size

The sample size is calculated in order to compare the OS between patients randomized to receive pegilodecakin in combination with FOLFOX versus FOLFOX alone. Approximately 566 patients will be randomized to the 2 arms in a 1:1 ratio to observe at least 393 death events. Assuming a median OS time for the FOLFOX arm of 5.9 months, 393 events are needed to detect a 35% increase with 85% power using a log-rank test (2-sided) with an overall type 1 error of 0.05, which corresponds to a median survival of 8 months in the pegilodecakin in combination with FOLFOX arm (hazard ratio [HR] = 0.7375).

7.4. Planned Interim Analyses/Final Analysis

Two interim analyses are planned for this study. The first interim analysis will be performed when approximately 60 randomized patients have had the opportunity to complete 4 months of therapy from the date of randomization. The nominal significance will be calculated based on O'Brien and Fleming alpha spending function in EAST v6.4. The second interim analysis is planned after approximately 276 deaths (70% of the 393 events) have been observed. The stopping boundaries will be derived based on the actual observed deaths at the first and second interim analysis. If the second interim analysis is performed approximately at 276 deaths, the study could be stopped by the DMC for efficacy if the p-value is <0.015. The nominal significance level for the final look at OS after 393 events would then be 0.045.

	Interim Analysis 1	Interim Analysis 2	Final Analysis
Conditions	Approximately 60 randomized patients who have had the opportunity to receive 4-months of therapy	Approximately 276 OS events	393 OS events
Alpha level	0.0001a	0.015	0.045
Upper HR Boundaries	2.145	1.342	1.224
Lower HR Boundaries	0.466	0.745	0.817

Table JZGB.7.1.Schedule of Analyses

Abbreviations: HR = hazard ratio; OS = overall survival.

^a A very small alpha is planned to be spent at the first interim analysis. Hazard Ratio boundaries are calculated based on the alpha spent. Hazard ratio (HR) boundaries are calculated based on the alpha spent. The O'Brien-Fleming (OBF) spending function is used to allocate the alpha at analysis 2 and final analysis with total alpha level of 0.0499. The actual alpha at each interim analysis will be recalculated based on the number of events observed at each analysis. The HR boundaries are for reference only and they are not for decision making.

7.5. Randomization, Stratification

Patients will be randomized in a 1:1 ratio to pegilodecakin combined with FOLFOX or FOLFOX. The randomization will be stratified by 2 stratification factors:

- prior single agent gemcitabine therapy versus gemcitabine/nab-paclitaxel therapy
- North America versus Europe versus APAC

Strata from IVRS (randomized strata) will be used in all efficacy analysis.

7.6. Methods for Handling Missing Data

In general, missing data will be treated as missing and no data imputation will be applied, unless otherwise specified. Additional data handling rules including those for imputation of partially missing dates are provided in a separate document pertaining to programming specifications.

8. Patient Disposition

8.1. Disposition

Patient disposition will be summarized using the All Enrolled population, randomized or not randomized, along with the reason for not being randomized.

The number or patients in the study populations, ITT, Safety, Per Protocol (PP) and reasons for exclusion from the PP population (no baseline scan, no post-baseline scan, or has a major protocol deviation) will be presented by randomized arm.

The number and percentage of patients who continued on pegilodecakin maintenance cycles will be summarized and the number and percentage of patients in survival follow-up will be summarized as well.

A summary table of randomized stratifications (geographic region and prior therapy) by treatment arm will be provided for the ITT population using data provided by IVRS. This data will be compared to data provide via the electronic case report form (eCRF) for consistency. If any inconsistencies exist between the IVRS and eCRF data, a separate summary for the stratification factors will be provided using eCRF data.

A table summarizing study discontinuation, along with reason for discontinuation will be provided. Primary reason of study discontinuation may include 1 of following: withdrawal of consent; death; discontinuation of the study at the request of ARMO, a regulatory agency, or an institutional review board (IRB)/independent ethics committee (IEC); and other. This analysis will be performed only on the ITT population.

A summary table of patients treated, treatment ongoing, treatment discontinued, along with reasons of treatment discontinuation for each study drug: pegilodecakin and components of FOLFOX (oxaliplatin, Leucovorin, and 5-Fluorouracil) will be provided. This table will be performed only on the Safety population. In addition, the number of patients who received maintenance therapy will also be summarized.

All disposition data will also be provided via data listings.

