| Final Analyses | 
randomized patients have had the opportunity to receive 4 months of therapy. The purpose of the first interim analysis is to evaluate PK exposure-safety and to perform a PK exposure-efficacy analysis to derive a Go/No-Go decision. The criteria for Go/No-Go decision will be developed with the DMC and incorporated into the DMC charter. This interim analysis is not designed to stop the study early for outstanding efficacy. Based on review of the PK exposure-safety and PK exposure-efficacy on the aggregated data of composite efficacy endpoints, the DMC will recommend continuing the trial, amending the study protocol, or stopping the study. The study will continue to enroll while this analysis is being completed.
 
A second interim analysis will occur after approximately 276 deaths (70% of the 393 required deaths for final analysis) have occurred. The purpose of this interim analysis is to evaluate the safety and efficacy with the possibility of claiming superiority.
 
The final analysis will be conducted when at least 393 deaths occur.
 |
| Statistical Methods Efficacy Analyses | 
The primary efficacy analyses will be performed based on the Intent-to-Treat (ITT) population. Sensitivity analyses of all efficacy endpoints based on the Per-Protocol population will also be performed to confirm results obtained using the ITT population.
 
The primary efficacy endpoint is overall survival in this Phase 3 study.
 
Overall survival will be compared in the 2 randomized treatment arms at the interim and final analyses using a 2-sided log-rank test, stratified by 2 IVRS stratification factors: prior gemcitabine-containing regimen; gemcitabine versus gemcitabine/nab-paclitaxel and North America versus Europe versus APAC. Patient survival will be summarized by median survival time and 95% CI based on the Kaplan-Meier method. Progression-free survival will be summarized in the same manner as overall survival. Objective response rate will be summarized and compared using a Cochran-Mantel-Haenszel 2-sided test stratified by the Randomization stratification factors.
 |

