7.3 Analysis Populations

- Intent-to-treat population: All patients who are randomized, with study drug regimen assignment designated to initial Randomization, regardless of whether patients receive any study drug(s) or receive a different drug(s) from that to which they were randomized. This is the primary dataset for analyses of efficacy and baseline disease characteristics.
- Safety Population: All patients who receive any amount of study drug(s) with study drug assignment designated according to actual study drug(s) received. This is the primary dataset for treatment administration/compliance and safety.
- Per-Protocol Population: All patients who are in the Safety population and have no major protocol deviations.

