7.8 Sensitivity Analysis

Sensitivity analyses will be undertaken for calculation of the primary endpoint in order to evaluate the robustness of the analysis. Of specific note, OS sensitivity analyses will be performed in the following subgroups of the ITT population:

- Per protocol population

Other sensitivity analyses include:

- Defining survival time as the time from the date of study enrollment to the date of death due to disease
- Censoring patients that started additional anticancer therapy.

Further details can be found in the SAP.

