10.1.4.1. Dose Reductions

Each drug component may be reduced. Number of patients with at least 1 dose reduction, reason for reductions, and number of dose reductions will be summarized for each treatment arm for

each component of treatment. Each FOLFOX dose reduction level is defined in protocol Table 12.

11. Efficacy Analysis

All efficacy analyses will be based on the ITT population.

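### SAP 8.1 makes a missing scan a ground for exclusion from the per-protocol population, contrary to SAP 7.1 and protocol 7.3; the post-baseline part would drop early deaths from the per-protocol OS analysis that the protocol requires

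*SAP*

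**What the plan says.** The documents describe the PP population in three places.

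- Protocol 7.3: "Per-Protocol Population: All patients who are in the Safety population and have no major protocol deviations".
- SAP 7.1 repeats this: "Per-Protocol Population: All patients who are in the safety population and have no major protocol deviations". It then lists five major deviations, none of which is a missing post-baseline scan, and adds that "This is not an exhausted list and may be amended over the course of the trial".
- SAP 8.1, on the disposition tables, refers to "reasons for exclusion from the PP population (no baseline scan, no post-baseline scan, or has a major protocol deviation").

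SAP 7.1 also has a separate set that does carry a scan requirement: "Response evaluable population includes patients who have at least 1 baseline tumor scan and 1 adequate postbaseline tumor scan".

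On use of the PP population, the protocol synopsis states that "Sensitivity analyses of all efficacy endpoints based on the Per-Protocol population will also be performed". Protocol 7.8 states that "OS sensitivity analyses will be performed in the following subgroups of the ITT population", and the PP population is the only one named there. The SAP takes a different line. Section 11 opens with "All efficacy analyses will be based on the ITT population", and the three OS sensitivity analyses in SAP 11.3.5 do not include one in the PP population.

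**The concern.** SAP 8.1 gives three grounds for exclusion where SAP 7.1 and protocol 7.3 give one beyond being treated. A programmer cannot follow both sections.

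The two extra grounds differ in kind. A missing baseline scan is settled before randomization. A missing post-baseline scan is settled afterwards and can be caused by death, which is the OS event. If SAP 8.1 is followed, patients who die before their first scan drop out of a supportive OS analysis because they died. Both medians would then be inflated. If treatment has no early benefit, or does early harm, the PP hazard ratio would also look more favourable than the ITT one. The protocol presents the PP analysis as a way to confirm the ITT result, so its population should not be selected on outcome.

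**Working it through.** **Inputs.** Median OS of 5.9 and 8 months, HR 0.7375, 393 deaths, 85% power, two-sided 0.05, 566 patients at 1:1 (SAP 7.3; 283 per arm in the protocol synopsis). First scan at week 8 ± 3 days, so day 53 to 59 (protocol synopsis and 6.4). Enrolment over 25 months (protocol 2.3.4). One month = 30.4375 days (SAP 7.2). Assumptions: exponential survival, no dropout, uniform accrual.

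**1. The plan's own figure.** 5.9/8 = 0.7375. For this HR at 85% power and two-sided 0.05, the Schoenfeld formula gives 388 events and the Freedman formula 394. The stated 393 is reproduced.

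**2. Deaths before the first scheduled scan.** Proportion = 1 − exp(−ln 2 × t / median), with t = 56/30.4375 = 1.84 months.

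- Control: 1 − exp(−0.6931 × 1.84/5.9) = 19.4%; 283 × 0.194 = 55.
- Arm 1: 1 − exp(−0.6931 × 1.84/8) = 14.7%; 283 × 0.147 = 42.
- Total: about 97 of 566 (17.1%), or 97/393 = 25% of the planned deaths. Day 53 gives 92 and day 59 gives 101.

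This is an upper bound, because it treats every early death as having no scan. If only 25%, 50% or 75% lack one, about 24, 48 or 73 patients are removed.

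**3. Medians if all are removed.** An exponential distribution has no memory, so the median among day-56 survivors is 1.84 + 5.9 = 7.7 months in control and 1.84 + 8 = 9.8 months in Arm 1. Each rises by about 1.8 months.

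**4. Hazard ratio.** Let f be the share of early deaths excluded, taken as equal in both arms. Before day 56 the expected risk set in arm g is R_g(t) = S_g(56) + (1 − f)(S_g(t) − S_g(56)), and the expected deaths d_g(t) are multiplied by (1 − f). After day 56 nothing changes. The large-sample Cox estimate θ solves Σ[d₁ − (d₀ + d₁)·θR₁/(R₀ + θR₁)] = 0, with R and d weighted by the share of patients whose follow-up reaches t.

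The cut-off is month 26.8, where the design expects 393 deaths. The proportion dead in an arm with hazard h is 1 − [exp(−1.8h) − exp(−26.8h)]/(25h). This is 0.739 in control (h = 0.1175) and 0.650 in Arm 1 (h = 0.0866), and 283 × (0.739 + 0.650) = 393.

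| Assumed HR before / after day 56 | ITT | 25% excluded | 50% | 75% | 100% |
|---|---|---|---|---|---|
| 0.7375 / 0.7375 | 0.74 | 0.74 | 0.74 | 0.74 | 0.74 |
| 1.0 / 0.7375 | 0.80 | 0.79 | 0.77 | 0.76 | 0.74 |
| 1.5 / 0.7375 | 0.93 | 0.90 | 0.85 | 0.80 | 0.74 |

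For the first row, simulated data with 15,000 patients per arm agree (0.73 in ITT, 0.74 after full exclusion). The early hazard ratios of 1.0 and 1.5 are assumptions; the documents give no such values. The ITT column also depends on follow-up: with 24 months for every patient, the last row starts at 0.88 instead of 0.93.

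**The case against.** The strongest reply is that no analysis specified in the SAP uses the rule. SAP 11 rests all efficacy analyses on ITT, and the PP population appears only in the disposition and deviation displays. The wording is a parenthesis in a table description, while SAP 7.1 is the defining section. The scan phrases match the response-evaluable population, so they may be leftover text. This stands as a limit on severity. It does not remove the problem, because the protocol does require PP analysis of OS and the SAP holds two definitions for it. The open-ended deviation list in SAP 7.1 does not reconcile them either, since SAP 8.1 names the scan reasons as alternatives to a major deviation.

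A second reply concerns size. Protocol 6.4 requires an unscheduled scan at clinical progression, protocol 6.5 an end-of-treatment assessment if none was done in the previous 4 weeks, and eligibility a life expectancy of at least 4 months. This stands: 19% and 15% are ceilings.

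A third reply is that a missing baseline scan involves no conditioning on outcome and overlaps the SAP 7.1 deviation for lack of measurable disease. This also stands. The case against that reason is one of consistency only.

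A reader might infer that the rule hides excess early mortality in Arm 1. The documents do not support that. The primary OS analysis is ITT, SAP 12.1.4 summarises deaths in ITT by period, and PP exclusions are tabulated by arm with reasons (SAP 8.1) and listed (SAP 8.2). Nor do the documents show that such harm exists.

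**Conclusion.** The contradiction is real and should be settled before results are known. Following SAP 8.1 would make the protocol-required PP OS analysis depend on surviving to a scan. At most about 97 of 566 patients would be removed, with medians about 1.8 months higher if all were. This rests on exponential survival at the planned medians and on no early death having a scan.

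A reader might go further and infer that such an analysis could never confirm the ITT result. That is too strong. Under the design's own proportional hazards the HR stays at about 0.74 with or without the exclusion. It departs from ITT only if the early effect is absent (ITT about 0.80, PP 0.79 to 0.74) or adverse (for an assumed early HR of 1.5, ITT about 0.93, PP 0.90 to 0.74). The primary test and the ITT death summary are unaffected. This is a correction that should be made to a supportive analysis, not a threat to the trial's main conclusion.

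**What to change.** 1. In SAP 8.1, delete the missing post-baseline scan from the PP exclusion reasons.
2. Delete the missing baseline scan as well, for consistency with SAP 7.1. Alternatively, list it in SAP 7.1 as a baseline eligibility deviation.
3. Keep both scan requirements for the response-evaluable population only.
4. Add the PP analysis of OS required by protocol 7.8 and the synopsis to SAP 11.3.5, on the SAP 7.1 definition, and amend the opening sentence of SAP 11 to allow for it.

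The cost is a few lines of SAP text and one supportive analysis that the protocol already commits to. No new data, patients or alpha are needed.
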